4.6. SUBJECT WITHDRAWAL CRITERIA

Each subject may withdraw consent at any time during the study without penalty or loss of benefit to which the subject is otherwise entitled. Counseling about the subject's health will be provided by the PI or Co-Investigator if he/she decides to discontinue participation in the study. Medical advice regarding what is in the best interest of the subject will be provided.

The Investigator can withdraw a subject if, in his or her clinical judgment, it is in the best interest of the subject or if the subject cannot comply with the protocol. The PI may discontinue the subject's activity without the subject's consent if any of these criteria are met:

- The discovery or development of any health condition with a subject that would make his/her continued participation in the protocol dangerous to himself/herself.
- The failure of the subject to comply with the requirements of the protocol.
- Any significant finding that, in the opinion of the Investigator, would increase the risk of the subject having an adverse outcome from further participation in the study.

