3. STUDY DESIGN

3.1. STUDY ENDPOINTS

3.1.1. Primary Safety Endpoints

- Incidence and severity of solicited injection site AEs (arm pain, local tenderness, erythema (redness), induration (swelling/firmness) and systemic AEs (objective fever, subjective fever, chills, sweats, headache, myalgia, arthralgia, fatigue, nausea, vomiting) and neurological AEs (blurry vision, changes in balance or coordination, confusion, disorientation, dizziness, severe headache, shaking or body tremors, slurred speech, tingling or numbness, weakness or feeling weak) between days 1 and 8, and days 9-15 after vaccination, per treatment group (active vaccination versus placebo) and stratified by relatedness.
- Incidence and severity of unsolicited AEs between days 1-8, days 9-15, and up to day 29 after vaccination, per treatment group (active vaccination versus placebo) and stratified by relatedness.
- Incidence and severity of arthritis and skin/mucosal lesions up to day 29 after vaccination using standard case definitions and stratified by relatedness. This includes where possible quantitative reverse transcription polymerase chain reaction (RT-qPCR) for detection of PHV01 and lesion biopsy for histopathology.
- Incidence of SAEs observed up to day 181 and stratified by relatedness.
- Incidence and severity of MAAEs observed up to day 181 and stratified by relatedness.
- Physical and neurological examination results, vital signs, normal and abnormal clinical laboratory values (hematology and clinical chemistry, urinalysis).
- Incidence of adverse events of special interest (AESIs), to include pneumonitis, acute respiratory distress syndrome, multiorgan failure, a hemorrhagic diathesis, certain neurologic events (encephalitis, myelitis, aseptic meningitis, optic neuritis, transverse myelitis, generalized convulsions, Guillain-Barré Syndrome, acute disseminated encephalomyelitis), thrombocytopenia, anaphylaxis, and vasculitides.

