3.7. DISCONTINUATION CRITERIA

3.7.1. Discontinuation of an Individual Subject

As there is only 1 dose of study vaccine administered, there are no discontinuation rules for an individual subject.

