4.6.1. When and How to Withdraw Subjects

A subject may end his or her participation in the study at any time. If a subject withdraws, the Investigator will make a reasonable effort to determine the reason for the withdrawal from the study and to complete a final follow-up visit following the outline for the next scheduled visit as described in Section 5.1.3. Telephone calls, registered letters, and email correspondence are considered reasonable effort. For subjects leaving the study, a targeted examination may be performed, if medically indicated and if permitted by the subject.

Subjects who are withdrawn for SAE/AEs will be clearly distinguished from participants who are withdrawn for other reasons. Information relevant to the withdrawal will be documented in the appropriate section of the eCRFs. The Investigator will document whether the decision to withdraw from the study was made by the subject or the Investigator and which of the following possible reasons was responsible for withdrawal: SAE, Non-serious AE, Protocol violation (e.g., poor compliance with study visits), Consent withdrawal, not due to an AE, Moved from the study area, Lost to follow-up, Other (specify). If a subject meets withdrawal conditions for a concomitant medication violation or noncompliance, this should clearly be stated in the source document and the study termination eCRF.

When a subject withdraws due to an AE or is withdrawn by the PI due to an AE, the SRC and the Sponsor must be notified within 48 hours (Table 5). Investigators must follow the specific policy at each institution regarding the timely reporting of AEs and SAEs to the IRB. In all cases, the PI will make a reasonable effort to complete study termination procedures.

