4.6.4. Follow-up for Withdrawn Subjects

Investigators will follow subjects who are withdrawn as a result of an SAE/AE until the event has returned to normal or stabilized, the event is otherwise explained, or the subject is lost to follow-up.

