6.7.2.2. AE-Related Withdrawal of Consent

Any AE-related withdrawal of consent during the study must be reported *immediately* (within 72 hours of identification) by email or telephone to the Sponsor's representative/designee. Report the withdrawal to the IRB in accordance with IRB policy.

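### Investigator withdrawal after the single dose leaves new SAEs, MAAEs and AESIs uncollected up to Day 181, while the subject stays in the safety denominator

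*Protocol*

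**What the plan says.** **Withdrawal.** Protocol 3.7.1 states: "As there is only 1 dose of study vaccine administered, there are no discontinuation rules for an individual subject". Protocol 4.6 states: "The PI may discontinue the subject's activity without the subject's consent if any of these criteria are met". The three grounds are:
- "The discovery or development of any health condition with a subject that would make his/her continued participation in the protocol dangerous" to the subject;
- failure to comply with the protocol;
- a significant finding that, in the investigator's opinion, "would increase the risk of the subject having an adverse outcome from further participation in the study".

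None is limited to the period before dosing. Section 4.6.3 allows up to 3 vaccinated subjects to be replaced if withdrawn or lost before Day 29, so withdrawal after dosing is foreseen.

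**What continues afterwards.** Section 4.6.4: "Investigators will follow subjects who are withdrawn as a result of an SAE/AE until the event has returned to normal or stabilized" (or is otherwise explained, or the subject is lost). Section 6.6.2 follows SAEs to resolution. Section 4.6.2 reports all data up to withdrawal. Section 5.1.4 asks subjects who withdraw between visits to complete the next scheduled visit, at least 28 days after dosing, as their EoS visit.

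**What stops.** Table 2, footnote 5, records SAEs, MAAEs and AESIs until EoS. Section 6.6.2 adds that investigators need not actively look for SAEs in former subjects. Section 5.4.2, by contrast, says all subjects are followed to Day 181 at least.

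**Endpoints and analysis.** Protocol 3.1.1 lists as primary: "Incidence of SAEs observed up to day 181 and stratified by relatedness", with MAAEs over the same period. SAP 1.2.5.1 sets Day 181 for AESIs too. SAP 2.1 defines ASaT as everyone dosed who has on-study safety data, and SAP 4.4.2 reports simple subject incidence. SAP 3.9, on withdrawals, deals only with replacement, and SAP 3.10 makes in general no substitution for missing data.

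**Reporting.** For a withdrawal due to an AE, Section 4.6.1 says "the SRC and the Sponsor must be notified within 48 hours". Section 6.7.2.2 says "Any AE-related withdrawal of consent during the study must be reported", gives 72 hours, and does not name the SRC.

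**The concern.** Two of the three grounds in Section 4.6 concern the subject's health. If removal for those reasons also ends the search for new events, the missing follow-up may be related to safety, and a later SAE, MAAE or AESI could go unrecorded. The analysis would not show this. The incidence tables have no person-time or censoring rule for AEs, so a subject last seen near Day 29 is counted over Day 181 exactly like one observed throughout. In a first-in-human live-vaccine study with 10 subjects per dose, one such subject is 10% of a dose group.

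The documents also disagree. Section 5.4.2 promises follow-up of all subjects to Day 181, and Sections 4.6, 5.1.4 and 6.6.2 together allow it to end sooner.

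**Working it through.** **1. The plan's own figure.** Protocol 7.1 gives a 30.9% upper limit for 0 events in 10 subjects (two-sided 95% Clopper-Pearson); SAP 3.1 gives 11.6% for 0 in 30. With no events the limit is 1 − 0.025^(1/n).
- n = 10: 30.85%, matching 30.9%.
- n = 30: 11.57%, matching 11.6%.

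**2. Follow-up not covered.** Dosing is on Day 1, so 28 days after dosing is Day 29, and Day 1 to Day 181 spans 181 − 1 = 180 days.
- Last visit on Day 29: (181 − 29)/180 = 152/180 = 84% unobserved for new events.
- If that visit does not take place and contact ends on Day 15: 166/180 = 92%.
- If contact ends on Day 8: 173/180 = 96%.

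**3. How the subject is counted.** Suppose one of 10 subjects is withdrawn by the investigator and has no SAE up to the last visit, and the other nine have none to Day 181. The table shows 0/10, with an upper limit of 30.9%. Only nine subjects were observed to Day 181.

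**4. Precision with fewer subjects observed.** The documents give no withdrawal rate, so 1 or 2 is an assumption.

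| Subjects not observed | One dose group (of 10) | All vaccinees (of 30) |
|---|---|---|
| 0 | 30.9% | 11.6% |
| 1 | 33.6% (n = 9) | 11.9% (n = 29) |
| 2 | 36.9% (n = 8) | 12.3% (n = 28) |

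These limits apply to an event type with no occurrence. They measure lost precision. The bias from selective withdrawal would depend on who is withdrawn and what happens to them later, and the documents give neither.

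**5. The two reporting rules.** A subject who withdraws consent because of an AE falls under both Section 4.6.1 (48 hours, SRC and Sponsor) and Section 6.7.2.2 (72 hours, Sponsor's representative or designee, and the IRB under its own policy). One event therefore has two deadlines and two recipient lists, and the second omits the committee that clears each cohort under Section 3.7.2.

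**The case against.** A reader might infer that subjects with safety problems drop out of follow-up for both the Day 29 and the Day 181 endpoints. The documents do not support that.
- The event behind an SAE/AE withdrawal is followed until normal or stable. Arthritis and rash are followed to resolution (Sections 5.4.1 and 5.4.2). Data up to withdrawal are kept, so that event is counted in ASaT.
- The visit requested in Section 5.1.4 coincides with Visit 7, which includes the neurologic examination, safety laboratory tests, vaccinemia and shedding. Much of the Day 29 loss is thereby covered. The safeguard is incomplete: the subject is only asked, the wording speaks of subjects who withdraw and not of those withdrawn by the investigator, and Section 4.6.1 describes the final visit without the 28-day minimum.
- Replacement under Section 4.6.3 does not remove the original subject from ASaT.

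It may also be said that Sections 3.7.1 and 4.6 do not contradict each other, since the first can be read as concerning vaccination and the second study participation. That reading is fair. Nor does withdrawal after dosing end observation alone: Table 3 plans 107.7 mL of blood on Day 29 and 120 mL on Day 85, and arthrocentesis or biopsy is possible, so there can be good reason to stop procedures.

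Finally, withdrawal is permitted and not required, such subjects should be few, and the study is largely descriptive. All this limits the size of the point. It does not supply a provision for collecting new events after the early EoS visit.

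**Conclusion.** The point holds in a limited form. After investigator withdrawal the triggering SAE/AE is followed, but no section provides for active collection of new SAEs, MAAEs or AESIs from the last visit to Day 181. That is about 152 of 180 days if the visit falls near Day 29. The subject stays in the ASaT denominator and counts as free of later events, which conflicts with Section 5.4.2.

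This rests on two readings: that a withdrawn subject is a former subject in the sense of Section 6.6.2, and that the early visit closes the collection period in Table 2. Neither is spelled out, which is itself a reason to clarify.

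The limits of 33.6% and 36.9% should not be taken as evidence of bias. They show only the precision lost if 1 or 2 of 10 subjects were unobserved. The number of subjects affected and the size of any bias cannot be computed from the documents. The 48-hour and 72-hour rules are a separate, genuine inconsistency that does not affect endpoint ascertainment.

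**What to change.** Leave the investigator's withdrawal criteria in Section 4.6 unchanged.

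1. **Protocol.** Reconcile Sections 3.7.1, 4.6, 4.6.4, 5.1.4, 5.4.2 and 6.6.2. Extend 4.6.4 and 5.1.4 so that any dosed subject withdrawn by the investigator who has not withdrawn consent remains in SAE, MAAE, AESI and concomitant-medication follow-up through Day 181. Contact may be by visit or by telephone, a route the opening note of Section 5.1 already allows for missed visits. Say expressly that the Section 5.1.4 visit applies to investigator-initiated withdrawal.
2. **SAP.** In 3.9 or 4.4.2, state that events collected after such a withdrawal are included in the ASaT Day 181 incidences.
3. **Reporting.** Reconcile Sections 4.6.1 and 6.7.2.2 so that an AE-related withdrawal has one deadline and one recipient list.

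The cost is protocol and SAP wording plus a few telephone contacts for a rare subject. After Day 29 only the Day 85 and Day 181 contacts remain in the schedule, and Memory Aids to Day 181 are already planned.

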4.6.1. When and How to Withdraw Subjects

A subject may end his or her participation in the study at any time. If a subject withdraws, the Investigator will make a reasonable effort to determine the reason for the withdrawal from the study and to complete a final follow-up visit following the outline for the next scheduled visit as described in Section 5.1.3. Telephone calls, registered letters, and email correspondence are considered reasonable effort. For subjects leaving the study, a targeted examination may be performed, if medically indicated and if permitted by the subject.

Subjects who are withdrawn for SAE/AEs will be clearly distinguished from participants who are withdrawn for other reasons. Information relevant to the withdrawal will be documented in the appropriate section of the eCRFs. The Investigator will document whether the decision to withdraw from the study was made by the subject or the Investigator and which of the following possible reasons was responsible for withdrawal: SAE, Non-serious AE, Protocol violation (e.g., poor compliance with study visits), Consent withdrawal, not due to an AE, Moved from the study area, Lost to follow-up, Other (specify). If a subject meets withdrawal conditions for a concomitant medication violation or noncompliance, this should clearly be stated in the source document and the study termination eCRF.

When a subject withdraws due to an AE or is withdrawn by the PI due to an AE, the SRC and the Sponsor must be notified within 48 hours (Table 5). Investigators must follow the specific policy at each institution regarding the timely reporting of AEs and SAEs to the IRB. In all cases, the PI will make a reasonable effort to complete study termination procedures.

4.6.2. Data Collected for Withdrawn Subjects

All data collected up to the time of withdrawal, including any final evaluation and lab results that may be pending at the time of withdrawal, will be reported. Likewise, any specimens collected up to the time of withdrawal, including any sample collected for storage and use in future research, will be kept and utilized as outlined in the protocol and ICF. The study termination eCRF will be completed, with the reason for withdrawal specified.

If a subject withdraws consent but does not revoke the Health Insurance Portability and Accountability Act (HIPAA) authorization, PHV will have full access to the subject's medical records, including termination visit information. If a subject revokes only the HIPAA authorization, PHV will have full access to all the subjects' medical records prior to the date and time of written revocation.

4.6.3. Replacement of Subjects

To ensure that a required minimum number of subjects (36) are available for vaccination, any subject scheduled for vaccination who is not available at time of vaccination will be replaced with a screened and eligible alternate subject. If the replacement occurs after randomization, the replacement subject will be randomized to the same treatment group. Once vaccinated, up to 3 subjects may be replaced should they be withdrawn from the study or lost to follow-up before day 29.

4.6.4. Follow-up for Withdrawn Subjects

Investigators will follow subjects who are withdrawn as a result of an SAE/AE until the event has returned to normal or stabilized, the event is otherwise explained, or the subject is lost to follow-up.

5. TREATMENT OF SUBJECTS

5.1. DETAILED DESCRIPTION OF STUDY VISITS

Note: If a subject is not able to visit the study site for scheduled visits or due to transient circumstances not precluding continuation in the study, they are asked to contact the study site by telephone immediately. AE and concomitant medication details may be collected during a telephone call. It may not be possible to collect all clinical laboratory samples or conduct clinical assessments during this time, but the study site is asked to make every effort to collect and record all possible available information designated by the protocol. If alternative arrangements can be agreed for the sample collection or clinical assessments, the details should be documented.

5.1.1. Screening Visit

Visit 1/Screening (days -28 to -1)

Reconfirm interest in this study before starting; significant time and travel is required in the first month and multiple resources are committed by the site and Sponsor to each subject.

Screening and enrollment procedures will be the same for all potential subjects. Any potential subject falling outside the 28-day window will require rescreening. The following procedures will be performed during the screening/briefing visit:

- Explain the study and review the informed consent with subject. Obtain written informed consent for participation in the clinical study and for HIV testing. Provide a copy of the signed ICF to the subject.
- Collect demographic information and medical history (including concomitant medications).
- Check each inclusion and exclusion criterion.
- Weight, vital signs, and physical examination, including baseline neurologic examination
- Sample collection including:
 - o Complete blood count (CBC) with WBC differential
 - o Coagulopathy tests, including prothrombin time (PT), partial thromboplastin time (PTT), and international normalized ratio [INR]
 - o Serum chemistry metabolic panel, including at a minimum creatinine, glucose, AST, ALT, and total bilirubin (plus direct bilirubin if elevated)
 - o Pregnancy test (serum) (all female subjects who may become pregnant see below)
 - Urinalysis
 - o Viral serologies (HIV-1, HIV-2, hepatitis C [HCV], hepatitis B surface antigen [HBsAg])

Potential subjects will be notified of their eligibility as soon as laboratory results are available and an assessment can be made by the Investigators. If determined to be eligible, subjects will be scheduled for their initial vaccination (day 1, Visit 2).

Regardless of eligibility, individuals will be informed of any significantly abnormal test results in an expeditious manner via telephone, in person, or by written communication. Appropriate counseling will be given regarding necessary medical follow-up. Participants may rescreen once.

5.1.2. Treatment Visit

Visit 2/Enrollment and Injection (day 1)

Subjects will have only 1 dosing visit during the study. Each subject will receive a 1 mL IM injection of PHV01 or placebo into the outer aspect of the subject's upper arm (deltoid area).

The following procedures will be performed during the injection visit, prior to the injection:

- Vital signs check
- Review of inclusion/exclusion criteria to confirm eligibility, then randomize
- Review of any AEs (including concomitant medications) since previous visit
- Directed physical examination (including proposed injection site)
- Rapid antigen test for SARS-CoV-2
- Urine pregnancy test (females only)
- Human leukocyte antigen (HLA) B27 typing (once only)
- Hematology, chemistries, and coagulation tests as above
- Collection of baseline samples for:
 - o PHV01 antibody, including sera for rheumatology and dermatology assessments
 - o PBMCs
 - o Transcriptomics
 - o Vaccinemia
 - Cytokines levels

Injection Procedures

- Administration of PHV01 or placebo
- Provision of emergency contact card
- Post-injection observation period: examination of injection site and vital signs check (≥60 minutes and ≤90 minutes post-vaccination)
- Explanation of the Memory Aid (see Section 5.4), distribution of thermometer and ruler, and review of use. Subjects are to record the severity of symptoms, including injection site reactions, joint-related AEs (joint pain, pain on motion of joints, joint swelling, joint tenderness), neurological issues, and rash, with the concomitant medications taken, and body temperature.

Subjects will remain in the clinic on day 1 for lunch and a blood draw at $6h \pm 1h$, including;

- Vital signs check
- Review of any immediate AEs or change in health status
- Collection of samples for vaccinemia, shedding, and transcriptomics

5.1.3. Follow-Up Visits

Subjects will be followed closely in the first month in the clinic, then at 3 and 6 months as outlined below. They will use a Memory Aid with a list of graded solicited symptoms, including injection site reactions, self-recorded body temperature, and concomitant medications to help record any issues. There is space for unsolicited symptoms as well. This should be filled out daily until day 14, then 3 times a week until day 29, then once a week until day 181. Subjects should pay special attention to neurological symptoms, joint-related symptoms (joint pain, pain on motion of joints, joint swelling, joint tenderness) and rash.

If an AE of post-vaccination arthritis or rash is reported, the appropriate evaluations will be triggered as outlined in Section 6.2 and Section 6.3, respectively. Always swab an open skin lesion or aspirate vesicular fluid if present, along with oral mucosa. Swabs should be placed in Viral Transport Medium and frozen at < -60°C. The following procedures will be performed during each follow-up visit:

Visits 3-6/Interim Evaluation (days 2, 4, 8, and 15)

- Vital signs check
- Review of subject's AEs, concomitant medications, and any change in health status since previous visit including joint or neurological symptoms and rash
- Perform directed history and physical, including neurologic examination at discretion of the Investigator to assess possible AEs. Document abnormalities, including neurological, joint, or skin exam, signs if symptoms are present. Photograph rash if present.
- Hematology, chemistries, coagulation tests, and urinalysis as above (days 4 and 8 only)
- Collection of samples for:
 - o PHV01 antibody (day 8 and 15 only)
 - o PBMCs (day 8 only)
 - o Transcriptomics at each visit
 - o Vaccinemia and shedding at each visit
 - o Cytokine levels (days 4 and 8 only)
- At the day 4 visit, please remind subjects to call the site if they have any joint-related AEs, rash or neurologic complaints.

Visit 7/Final Acute Evaluation (day 29)

- Vital signs check
- Review Memory Aid for days 1-29
- Review of subject's AEs, concomitant medications, and any change in health status since previous visit including joint or neurological symptoms and rash
- Perform directed history and physical, as well as a neurologic examination. Document joint and skin exam if symptoms present. Photograph rash if present.
- Hematology, chemistries, coagulation tests, and urinalysis as above (days 4 and 8 only)
- Urine pregnancy test (females only)

- Collection of samples for:
 - o PHV01 antibody
 - o PBMCs
 - Vaccinemia and shedding
 - Cytokine levels

Visit 8/3-month Follow up (day 85)

- Vital signs check
- Review Memory Aid for days 29-85, including any unsolicited symptoms
- Review of subject's AEs, concomitant medications, MAAEs, SAEs, AESIs, and change in health status since previous visit
- Perform directed history and physical
- Collection of samples for:
 - o PHV01 antibody
 - o Blood for research (100 mL)

Visit 9/6-month Follow up (day 181)

- Vital signs check
- Review Memory Aid for days 85-181, including any unsolicited symptoms
- Review of subject's AEs, concomitant medications, MAAEs, SAEs, AESIs, and change in health status since previous visit
- Perform directed history and physical
- Collection of samples for:
 - o PHV01 antibody

Visit 9 (day 181) will be the End of Study (EoS) visit for all subjects. Subjects completing this visit will be considered to have completed the study. Subjects with an ongoing AE at this visit will be followed until the event has returned to normal or stabilized, the event is otherwise explained, or the subject is lost to follow-up.

